#### 6.4. Sensitivity analysis

# See Handling of Deviations and Protocol Amendments 9.7

# 6.5. Assessment of cost and cost-effectiveness

Once we have established the effectiveness of the patient navigation program, we will assess costs and costeffectiveness from the health-plan perspective, both overall and by risk stratum (high- vs. moderate- vs. lowprobability of adherence). We will follow best practices and be guided by previous economic analyses of patient navigation for CRC screening follow-up. First, we will assess the costs of implementing and maintaining the patient navigation program and estimate how costs of patient navigation differ when delivering the service to all patients, versus just those who have a moderate or low probability of undergoing a colonoscopy. Next, using the framework of cost-effectiveness, we will estimate the incremental cost-effectiveness ratio (ICER) as: (1) cost per additional completed colonoscopy, (2) cost per additional adenoma detected, and 3) cost per additional cancer detected.

Consistent with our previous economic evaluation of CRC screening interventions, costs collected will include those of (1) medical care related to cancer detection (e.g., colonoscopy, re-screening) and (2) the intervention delivery. Costs of cancer care will not be included. We will identify follow-up colonoscopy events and rescreening using EHR data, and apply costs using standard Medicare fee schedules. Intervention delivery costs will include health plan project management, patient identification, patient tracking, and navigator time, among others. Resources used to deliver the intervention will be identified using staff logs, interviews, and budget information. We will use national sources for wage rates for clinic and other staff (e.g., programmer) time. Research and non-research costs will be separated after discussion with intervention and project staff, and we will undertake a sensitivity analysis focused on replication costs (those costs most likely to be part of implementation). We will focus on near-term (within 1 year of positive FIT) costs and effects of the program, as our experience suggests those analyses are of most interest to decision-makers; costs will not be discounted owing to the 1-year timeframe.

We will estimate the intervention's ICERs using net benefit regression methods and will construct costeffectiveness acceptability curves to illustrate the probability of navigation being cost-effective across a range of willingness-to-pay values. Using net benefit regression, we will evaluate differences in cost-effectiveness by subgroups, including baseline probability of adherence (moderate vs. low). After inspection, costs between the arms will be compared using methods appropriate for cost data (e.g., right-skewness, censored follow-up time).

While cost-effectiveness is critical to understanding the value of screening improvements, the costs of the navigation will vary depending on the amounts of specific services delivered. To address this, we will develop scenarios to illustrate how intervention costs change when fixed costs are spread over differing population sizes, and how patient population factors influence variable costs. Other scenarios will examine whether costs of navigation can be offset by gains to health systems, such as fewer repeat colonoscopies because of adequate colonoscopy prep and fewer late cancellations and missed appointments/no-shows. We will also assess the number needed to treat (e.g., patient navigation) in each probability stratum to achieve a successful follow-up colonoscopy. (See Handling of Deviations and Protocol Amendments 7.6)

# 7. Data auditing and validation

# Fidelity assessment and intervention dose (scientific rigor).

Our fidelity assessment will be designed in accordance with established methods outlined by the NIH Behavior Change Treatment Fidelity Workgroup and will focus on: (1) the accuracy of data capture for our primary and secondary outcomes (measurement fidelity), and (2) rigor and consistency with which the intervention is delivered (intervention fidelity). As part of intervention fidelity, we will assess the intervention dose. Intervention fidelity: To address intervention fidelity, research staff will monitor navigator calls with patients and provide feedback. A quality assurance tracker will be used by research staff to track content and timing of calls and identify areas for improvement. Any issues will be addressed during debrief meetings and booster training sessions.

- During the pilot, research staff will listen to a portion of patient calls for navigator coaching purposes.
- During the main trial, research staff will listen to 10 live calls every 3 months for the first year, and then 10 live calls every 6 months during the second year.

Qualitative patient interviews at the end of the program (n = 60) will gather patient-reported information on receipt of each call type, consistent with the NHCRCSP.

Intervention dose. As part of the fidelity assessment, we will track consistency of intervention dose: the number and content of phone calls delivered by patient navigators based on data collected from the patient navigation tracking system designed in REDCap®. The standard protocol includes six timed phone calls that address predefined content areas; thus, dose will be calculated as the proportion of phone calls completed and/or content areas addressed (with 6 as the denominator).

| NAVIGATION PROTOCOL TOPIC AREAS                   | COMPLETE IF DELIVERED BY  |  |
|---|---|--|
| Topic 1 – Introductory Call                       | Within 1-7 days of navigator assignment                           |  |
| Topic 2 – Barrier Resolution Calls                | Flexible timing prior to procedure                                |  |
| Topic 3 – Bowel Prep Review Call                  | 5-7 days before colonoscopy                                       |  |
| Topic 4 – Day before Colonoscopy Check-In
Call | Afternoon or evening before colonoscopy (text message acceptable) |  |
| Topic 5 – Colonoscopy Check-In Call               | Day of colonoscopy (text message acceptable)                      |  |
| Topic 6 – Post-Colonoscopy Call                   | 2-4 weeks after colonoscopy                                       |  |

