#### 1. Study design and specific aims

Predicting and Addressing Colonoscopy Non-adherence in Community Settings (PRECISE) is an individualrandomized clinical trial of a patient navigation intervention versus usual care to improve participation in followup colonoscopy in a federally qualified health center. The study consists of two phases: **Phase I** (Aim 1) is a milestone-driven planning phase to externally validate the risk-prediction score, stratify patients' probability of adhering to follow-up colonoscopy, and adapt patient navigation materials for the local context. **Phase II** (Aims 2–3) is a large-scale, targeted patient-randomized controlled trial that will include ~1200 patients across ~32 clinics in western Washington State.

The study has the following aims:

**Aim 1:** Validate externally the predictive risk score using Sea Mar Community Health Center's robust data including 29,000 patients age-eligible for colorectal cancer screening; stratify patients according to risk of non-adherence to follow-up colonoscopy; and adapt patient navigation program for the local context.

Aim 2: Assess the effectiveness, costs, and cost-effectiveness of a centralized, phone-based patient navigation program for follow-up colonoscopy receipt for patients at moderate risk or high risk for non-adherence. (See Handling of Deviations and Protocol Amendments 9.1 and 9.2)

**Aim 3:** Assess differences in the intervention arms in secondary outcomes (e.g. time to colonoscopy receipt, noshow/canceled appointments, colonoscopy quality) and moderators of intervention effectiveness (e.g. probability level, intervention dose, and patient age, ethnicity, and sex) (See **Handling of Deviations and Protocol Amendments 9.3**)

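### Intervention dose is scored over a fixed 6 topics, four of which need a scheduled or performed colonoscopy, so the score partly reflects the outcome; Aim 3 still lists it as a moderator

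*SAP*

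**What the plan says.** SAP section 7 (fidelity assessment and intervention dose) sets out six navigation topics and states that "dose will be calculated as the proportion of phone calls completed and/or content areas addressed (with 6 as the denominator". The table beside it says when each topic counts as complete:

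- Topic 1: "Within 1-7 days of navigator assignment"
- Topic 2: "Flexible timing prior to procedure"
- Topic 3: "5-7 days before colonoscopy"
- Topic 4: "Afternoon or evening before colonoscopy (text message acceptable"
- Topic 5: "Day of colonoscopy (text message acceptable"
- Topic 6: "2-4 weeks after colonoscopy"

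No rule covers patients who are never scheduled or never scoped. The primary outcome (SAP 5.1) is a follow-up colonoscopy within 1 year of the abnormal FIT.

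Aim 3 in SAP section 1 includes "moderators of intervention effectiveness (e.g. probability level, intervention dose, and patient age, ethnicity, and sex". The moderator lists in 5.3 and 6.3 do not contain dose, nor does the heterogeneity list in section 3. Item 8.6, which records changes to the moderators, adds county and drops Hispanic ethnicity but does not mention dose.

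**The concern.** A fidelity measure should show how well the navigator delivered the programme. Here half of the score (Topics 3 to 5) is out of reach until a colonoscopy is booked, which is the step just before the outcome. A further sixth (Topic 6) is out of reach until the procedure has been done. A navigator who does everything possible for a patient who never schedules still scores that patient 2/6.

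Two things are at stake. First, the reported dose will look like incomplete delivery when some of the shortfall is simply patients without a colonoscopy. Second, Aim 3 still announces dose as a moderator while no method for it is written. The only dose variable the SAP defines would be associated with completion even if the calls had no effect.

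**Working it through.** The SAP gives no expected value for dose, so there is no stated figure to reproduce. The check takes the definition, finds its ceiling, and then shows what an association with the outcome would look like if delivery were unrelated to it.

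**Inputs.** From SAP section 7: six topics, of which two need no colonoscopy date, three need a date and one needs a performed procedure. From SAP section 4: completion c of 44% (usual care), 53.2% and 56.9% (navigation, without and with the design effect). From SAP section 3: 600 navigated patients. Assumed, because the documents do not give it: the share s of non-completers who ever had a date, taken as 0, 25% and 50%.

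**Ceiling by patient status.** Never scheduled: 2/6 = 0.33. Scheduled but not performed: 5/6 = 0.83. Performed: 6/6 = 1.00.

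**Mean dose under flawless delivery.** The ceiling for non-completers is u = (1 − s) × 2/6 + s × 5/6, which gives 0.333, 0.458 and 0.583. Mean dose = c + (1 − c) × u. For example, with c = 0.44 and s = 0: 0.44 + 0.56 × 0.333 = 0.627. A procedure done after the 1-year window is not modelled.

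| Completion c | s = 0 | s = 25% | s = 50% |
|---|---|---|---|
| 44% | 0.627 | 0.697 | 0.767 |
| 53.2% | 0.688 | 0.747 | 0.805 |
| 56.9% | 0.713 | 0.767 | 0.820 |

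Down each column, delivery is perfect throughout and only completion changes. Between 44% and 56.9% the score rises by 0.129 × (1 − 0.333) = 0.086 if s = 0, and by 0.129 × (1 − 0.583) = 0.054 if s = 50%.

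**Built-in association.** A simulation of 600 navigated patients (2000 runs) gave each deliverable topic with probability 0.8 (assumption), independently of outcome.

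- The correlation of the fixed-6 dose with completion was 0.89 to 0.90 at s = 0, 0.75 to 0.76 at s = 25% and 0.62 to 0.64 at s = 50%. A nominal 5% test rejected in 100% of runs.
- At c = 53.2%, patients with four or more topics completed in 100%, 85% and 74% (s = 0, 25%, 50%). Those with three or fewer completed in 10%, 12% and 15%.
- Dose restricted to Topics 1 and 2 had a correlation of about 0.00 with completion and rejected in 4.4% to 5.7% of runs.

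**Use as a moderator.** Section 6.3 tests a moderator by adding it and its product with arm to the primary model. Dose counts navigator contacts made after randomization, and usual-care patients get none, because section 3 keeps navigation and referral coordination separate. Dose therefore has no variation in the usual-care arm, and its product with arm is not an interaction.

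**The case against.** The strongest reply is that no dose-moderator analysis is specified. Sections 3, 5.3 and 6.3 all leave dose out, and section 6.3 speaks of patient characteristics, which dose is not. The Aim 3 mention sits in a list of examples that also keeps ethnicity and no-shows, both formally withdrawn later, so it may be leftover text. This stands, and it limits the weight of the point. It does not remove it, because section 8 records those other withdrawals and is silent on dose.

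A second reply is that section 7 uses dose descriptively, with no test or threshold, and that the share of the full programme received is a legitimate quantity. Monitoring of live calls, a quality tracker and 60 patient interviews also bear on delivery. This stands too, provided the score is labelled as programme received and not read as delivery quality.

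A reader might infer that dose separates completers from non-completers completely. The documents do not support that. A scheduled non-completer can reach 5/6, and the protocol's plan to collect no-shows and cancellations shows that such patients were expected. The SAP also expects some navigated patients never to be reached; any of them who completed would score close to 0.

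A reader might also infer that dose is simply caused by the outcome. Only Topic 6 follows the procedure. Topics 3 to 5 come before it and depend on scheduling, an intermediate step.

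The word joining calls and content areas in the dose rule leaves the numerator somewhat open. Credit given outside the table's timing would weaken the dependence, but the table ties completion to that timing.

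**Conclusion.** The point holds as a measurement defect and an unreconciled aim. The ceilings of 2/6, 5/6 and 6/6 follow from the SAP's own table. The understatement under flawless delivery depends on how many non-completers had a date: mean dose is 63% to 71% if none did, which is the extreme case, and 77% to 82% if half did. In every case shown the score falls short of 100% and moves with completion. Any association of this score with completion would be partly built in; the simulated correlations show that this could be strong, under an assumed delivery probability of 0.8.

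It would be wrong to conclude that the trial's effect estimate is compromised. The modified ITT comparison, the two per-protocol analyses, the secondary outcomes and the listed moderator analyses do not use the dose score. The change should be made, but it does not bear on the main result.

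**What to change.** 1. Report delivery topic by topic among navigated patients eligible for that topic: Topics 1 and 2 for all, Topics 3 to 5 for those with a colonoscopy date recorded by the navigator, and Topic 6 for those with a performed procedure.
2. If the fixed-6 score is kept, label it as a description of programme received, not as fidelity, and do not relate it to completion.
3. Remove intervention dose from the Aim 3 moderators and record the removal in section 8 alongside item 8.6.

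The cost is SAP wording and a recode of the REDCap tracking data. There are three small downsides. Dose is no longer one simple proportion. The eligibility-based figures measure delivery and not success at scheduling, so a navigator who reaches everyone but books no one would still score well on Topics 1 and 2. The Topics 3 to 5 denominator is only as good as the recorded dates; section 7 mentions only call number and content in the tracker, and item 8.3 dropped appointment data as unreliable across GI practices. The completeness of dates should therefore be reported with the figures.

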#### 8. Handling of Deviations and Protocol Amendments

- 8.1. Included all patients ages 50-75 with an abnormal FIT result, eliminated requirement of having moderate or high risk of follow-up colonoscopy non-adherence. Given the relatively low colonoscopy completion probability in the highest quintile group (65% vs. 93% estimated), we plan to randomize all eligible abnormal FIT patients. We will still prospectively calculate the patients' estimated probability of obtaining a colonoscopy, using the risk prediction model and preform subgroup analysis considering risk level as a moderator of effectiveness.
- 8.2. Eliminated cost and cost-effectiveness analysis. These analyses were eliminated because of COVID-19 resources constraints; through an official request to NCI dated 3/1/2021.
- 8.3. Eliminated no show/canceled appointments as a secondary outcome. We eliminated as an outcome noshow/canceled appointments because the number of referring GI practices would lead to inconsistencies and inaccuracies in the collection of these data.
- 8.4. Changed the randomization process. Following an electronic health record conversion, the original automated randomization in place at the partnering health center was disabled. As a result, from August 2021 through April 2022, patients were randomized weekly using the SURVEYSELECT procedure in SAS (Cary, NC).
- 8.5. Used Restricted Mean Survival Time for time-to-event analysis. To assess differences in time to colonoscopy completion between study arms (secondary outcome), we originally planned to use Cox proportional hazards and median survival time. Instead, we computed the log-rank test and restricted mean survival time (adjusted for county). Restricted mean survival time provides estimates of the mean time to event regardless of event rate whereas conventional median survival time is only computable when the event rate is 50% or greater. Moreover, restricted mean survival time is a more direct and interpretable measure of actual survival time, compared to a hazard ratio derived from a Cox model.
- 8.6. Added county and eliminated Hispanic ethnicity as potential moderators. County (8 unique counties in WA State) was added as a potential moderator, given possible variation by county in GI provider waittimes and other factors. We also eliminated Hispanic ethnicity as a moderator as it has a strong correlation with preferred language.
- 8.7. Added two sensitivity analyses to account for COVID-19-related care suspensions. Given possible impacts of COVID-19-related care suspensions, we performed a sensitivity analysis that assessed colonoscopy completion at 3 months, 6 months, 9 months, 12 months and 18 months following an abnormal FIT result. Additionally, we report number of completed colonoscopy every 3-months throughout the recruitment and evaluation intervals (July 2019 through December 2022).

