## 3. Randomization and blinding

Patients meeting clinical eligibility criteria will be randomized by the health center (Sea Mar) analyst to receive either the patient navigation intervention or usual care. Study identification numbers linked to patients will be uploaded into REDCap® on a weekly basis, for patients in the navigation arm, with date of abnormal FIT result. We anticipate that the time between patient identification and study randomization will take about 2 weeks. (See **Handling of Deviations and Protocol Amendments 9.4**)

Randomization will be performed using a stratified approach that considers patients' county of residence. We will use Sealed Envelope (London, UK) to randomize patients 1:1 to navigation or usual care in blocks of 4 to 8 individuals, stratified on county of residence. For practical reasons, neither the research team nor the clinic staff will be blinded to randomization assignment. However, measures have been taken to preserve as much blinding as possible. Staff trained in navigation will not perform colonoscopy referral coordination (as part of usual care). Patients randomized to patient navigation are removed from the referral coordinator list to eliminate potential outreach by referral coordinators. In this way, the patient navigation intervention will not be overlaid on usual care, as doing so would result in multiple contacts from multiple clinic staff. (Consistent with usual care, referral

coordinators will contact referred patients who have not completed a colonoscopy making up to three phone attempts; patients who are not reached will be sent a letter.)

The randomization will result in 600 patients assigned to the patient navigation arm and 600 assigned to the usual care arm. We will assess rates of colonoscopy receipt at 1 year overall, and will perform a heterogeneity of treatment effect analysis to assess differential effects by age, sex, ethnicity, language preference, insurance status, and probability of adherence (based on the risk model), using data from the electronic health record.

CHR analysts will assign a colonoscopy completion probability, based on the risk prediction model. These methods have been described previously.

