#### 6. Statistical Methods

#### 6.1. Primary outcome analysis

Primary analysis will rely on a modified intention-to-treat (ITT) that excludes patients from both arms who are randomized in error (determined to be ineligible based on information in the medical record that was missed during the eligibility determination process). Patients in the primary ITT data analysis will retain their randomization assignment irrespective of whether they received patient navigation. Two secondary per-protocol analyses are planned: one that excludes patients who were determined ineligible because they moved, or clinical reasons that occurred post-randomization; and a second that additionally excludes patients who were never reached by the navigator.

Sea Mar's EHR data will be transferred to CHR every 6 months via a secure file transfer. We will examine the distribution of all variables prior to analyses and verify all missing and out-of-range values. We will assess the ICC. If the ICC is .001 or above, we will use hierarchical generalized linear modeling to account for clustering of patients within clinics. If the ICC is less than .001, we will use adjusted logistic regression without accounting for clustering to optimize parsimony. Because the primary outcome is binary (i.e., follow-up colonoscopy, yes/no), we will use a model with a logit link and binomial distribution (i.e., multilevel logistic regression). The independent variable will be arm (dummy-coded) with usual care as the reference group. 'Clinic' will be modeled as a random effect. The model will include county as a covariate (fixed effect) as it was a stratification factor for randomization.

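### Randomization switched to weekly SURVEYSELECT draws for August 2021 to April 2022 with ratio, strata and odd-list rule unstated, and no analysis adjusts for that period

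*SAP*

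**What the plan says.** SAP Section 3 describes a single mechanism: an online randomization service used to "randomize patients 1:1 to navigation or usual care in blocks of 4 to 8 individuals, stratified on county of residence". It adds that "The randomization will result in 600 patients assigned to the patient navigation arm and 600 assigned to the usual care arm".

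SAP 8.4 then records that the automated system was disabled by an electronic health record conversion, and that "from August 2021 through April 2022, patients were randomized weekly using the SURVEYSELECT procedure in SAS". Nothing more is said of the replacement. The ratio, any stratification by county, any blocking and the treatment of odd-sized weekly lists are all unstated.

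The analysis sections are written as if there had been one mechanism. In 6.1, "The independent variable will be arm (dummy-coded) with usual care as the reference group", clinic is a random effect, and "The model will include county as a covariate (fixed effect) as it was a stratification factor for randomization". Section 5.2 names county as the covariate for all analyses. The restricted mean survival time analysis in 8.5 is adjusted for county. No analysis has a term for enrolment date, calendar period or randomization method.

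SAP 8.7 adds two analyses, introduced with "Given possible impacts of COVID-19-related care suspensions". One changes the outcome window (3 to 18 months). The other counts completed colonoscopies by quarter. Neither adjusts the comparison of arms for when patients were enrolled.

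**The concern.** Running blocks within county carry over from one week to the next, so an odd weekly intake is made up later and allocation stays close to 1:1 throughout. A stand-alone weekly draw cannot split an odd list equally. If a fixed rule always gave the extra patient to the same arm, allocation in these nine months would tilt one way while the rest of the trial stayed at 1:1. That arm would then hold a larger share of late-period patients.

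A tilt matters only if completion in the period differed from the rest. The documents make that plausible: the SAP refers to care suspensions, the protocol's modification table refers to pandemic interruptions, and the change of mechanism followed a change of the record system from which outcome ascertainment begins. Under both conditions, part of the period difference would appear as a treatment effect. County cannot stand in for period, since all counties may have enrolled in both.

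The SAP's own reason for adjusting for county is that it was part of the randomization scheme. For patients drawn in weekly lists, calendar time was part of the scheme too.

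**Working it through.** **Plan's own figure.** The documents give no number for allocation or completion by period. The only yardstick is SAP Section 4: 80% power for 9.2 points without a design effect and 12.9 points with one. Recalculation at 600 per arm from 44% gives 8.1 points without a design effect. With an ICC of 0.03 it gives 12.1 points (42 per clinic) or 11.7 (37.5 per clinic). The stated figures are therefore conservative. That is a separate matter, and they serve here only for scale.

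**Inputs from the documents.** 1200 patients (target); 8 counties (SAP 8.6); replacement period of 9 months (SAP 8.4); usual-care completion 44% (SAP Section 4).

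**Assumptions.** Recruitment at a uniform rate from July 2019 to April 2022, 34 months or about 148 weeks. (SAP 8.7 gives July 2019 to December 2022 for recruitment and evaluation together.) Completion differs by 10 points between periods. Weekly list sizes follow a Poisson distribution. Every odd list gives its extra patient to the same arm. Allocation outside the period is exactly 1:1.

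**Step 1, list size.** 1200/148 = 8.1 patients a week; over 8 counties, 1.01 per county-week. Share of patients in the period: 9/34 = 26%, or about 318.

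**Step 2, allocation under same-way rounding.** Favoured arm's share = 0.5 + P(odd)/(2m), where m is the mean list size and P(odd) = (1 − e^(−2m))/2.
- One list a week, m = 8.1: P(odd) = 0.50, share = 0.5 + 0.50/16.2 = 53.1%.
- Separate lists by county, m = 1.01: P(odd) = 0.434, share = about 71% (about 68% with uneven counties).

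**Step 3, bias.** Bias = (proportion of the favoured arm enrolled in the period − the same proportion in the other arm) × period difference in completion.
- One list a week: 168.6 v 149.0 in the period and 441.2 per arm outside it, so arms of 609.8 and 590.2. 168.6/609.8 − 149.0/590.2 = 0.2765 − 0.2525 = 0.024. Times 10 points = 0.24 points.
- By county at 71.4%: 226.8 v 90.8, arms of 668.0 and 532.0. 0.3395 − 0.1708 = 0.169. Times 10 points = 1.7 points.

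**Step 4, range.** Bias in points with 15% to 35% of patients in the period:

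| Allocation in period | 10-point period difference | 20-point period difference |
|---|---|---|
| 50:50 | 0 | 0 |
| 53:47 | 0.15–0.27 | 0.31–0.55 |
| 55:45 | 0.26–0.46 | 0.51–0.91 |
| 60:40 | 0.51–0.91 | 1.0–1.8 |
| 2:1 | 0.85–1.5 | 1.7–3.1 |

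**Step 5, effect on the test.** Ignoring clustering, SE = √(2 × 0.44 × 0.56/600) = 2.87 points. Nominal 5% two-sided error becomes 5.1% at 0.25 points of bias, 6.4% at 1 point and 10.7% at 2 points.

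**Step 6, chance imbalance.** With independent 1:1 assignment of 180 to 420 patients, the allocation share has SD √(0.25/n) = 3.7 to 2.4 percentage points. That is sampling variation and has no expected direction.

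**Step 7, cost of a period term.** Take 25% of patients in the period at 60:40. Information on the arm contrast is 630 × 570/1200 = 299.25 without the term and 180 × 120/300 + 450 × 450/900 = 297 with it, a loss of 0.75%.

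**The case against.** The strongest reply is that nothing has been shown to be wrong. SAP 8.4 reports a change of tool, not of ratio; Section 3 plans 1:1 with 600 per arm; and 5.2 and 6.1 still call county a stratification factor. Silence in 8.4 is a reporting gap, not evidence of unequal allocation. Splitting each weekly list about evenly would even tend to balance the arms over calendar time. All of this stands.

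A reader might infer that any departure from 1:1 in these months confounds arm with calendar time. The documents do not support that: a chance departure under valid randomization adds variance, not bias, and neither a systematic departure nor a period difference in completion is reported. A reader might also take 1.7 points as the likely size. It needs separate draws in every county every week and every odd patient sent to one arm, neither of which is stated. It would also leave arms of about 668 and 532 against the planned 600 each.

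The assumed inputs are fair targets too. No passage gives completion by period, says that recruitment ended in April 2022, or places the care suspensions within August 2021 to April 2022. The protocol's modification table speaks of getting closer to 1200, so that total is also a target.

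On the remedy, a prognostic covariate in a logistic model changes the conditional odds ratio being estimated. Parts of SAP Section 8 are in the past tense and the reference list includes a September 2023 paper, so analysis may already have begun. Adding the term to the primary model at that stage would be post hoc. This supports the sensitivity-analysis form, but it does not remove the case for running the analysis or reporting the counts.

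**Conclusion.** The point holds as an unverified risk with a cheap remedy. What is certain is that the replacement procedure is under-described, that all adjustment is for county only, and that the analyses in 8.7 leave the gap open. Bias needs two things together: a systematic tilt in allocation during the period and a different completion rate in it. The first is undocumented; the second is plausible but unquantified.

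On the simplest reading, one list a week with same-way rounding, the bias is about 0.2 points and type I error is barely affected. That rests on the assumed 26% share and 10-point period difference. It should not change how the main result is read. Only county-level draws with one-way rounding bring it above 1 point under those two assumptions. The allocation counts would show whether that happened.

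**What to change.** 1. In SAP 8.4, state for August 2021 to April 2022 the allocation ratio, whether draws were stratified by county, any blocking, and how odd-sized lists were split.
2. Report numbers allocated by arm, county and randomization period, from the randomization records.
3. Add a fixed effect for randomization period beside county in the primary and secondary models (5.2, 6.1, 6.2, 8.5). Levels: before August 2021; August 2021 to April 2022; any later enrolment as its own level. If the primary analysis is already locked, keep it unchanged and report the period-adjusted model next to it as a named sensitivity analysis.

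The cost is one table and one or two degrees of freedom, with under 1% of information lost at allocations up to 60:40 in the period. The term addresses the change of mechanism. It does not fully adjust for COVID-19 disruption before August 2021, because the first level pools enrolment before and during the early pandemic.
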